9.1 Sample size considerations

As the primary goal of this clinical trial is the safety and tolerability of long-term use of sargramostim in participants with mild-to-moderate Alzheimer's disease, a sample size of 42 participants (28 sargramostim-treated [1250 mcg/m²/ week subcutaneously], and 14 placebo equivalent) is considered sufficient to meet the endpoint of safety and is consistent with the lack of drug related SAEs in our recently-completed randomized, double blind, placebo-controlled trial of sargramostim in 40 (20 sargramostim-treated:20 placebo-treated) subjects with mild-to-moderate Alzheimer's disease.

Based on results for 40 participants at the EOT, 45-day follow-up, and 90-day follow-up in our recently completed sargramostim trial in participants with mild-to-moderate Alzheimer's disease, an effect size of

Mean Treatment Difference in Change from	Total	Number of	Number of		
Baseline to End of Treatment (Day 18)	Number of Patients	Sargramostim Patients	Placebo Patients	Alpha	Power
2	102	68	34	0.05	0.91
4	27	18	9	0.05	0.92
6	12	8	4	0.05	0.92
8	9	6	3	0.05	0.97

Table 1. Model for MMSE Total Score, Assumes no Treatment Effect at Baseline (successful randomization).

around 2–4 was predicted by the MMSE. We believe that the 42 participants (28 sargramostim-treated [1250 μ g/m²/week (178.57 μ g/m²/day subcutaneously seven days a week], and 14 placebo equivalent) who will be recruited for this study will provide sufficient power to allow valid analyses of the secondary and exploratory endpoints. Therefore, at least 42 individuals with mild-to-moderate Alzheimer's disease, age 60–85, of either sex, will be randomized (28 sargramostim participants and 14 placebo participants) for this proposed placebo-controlled study. For effect sizes of 2, 4, 6, or 8 (the expected treatment group differences in change between baseline and follow-up for MMSE total score), **Table 1** shows the number of participants required to achieve 91–97% power. Recruitment and treatment initiation will be timed to allow for the interim assessments before further participants are treated, thus assuring maximum early knowledge of any safety concerns.

The study will have two arms with participants assigned in permuted blocks examining placebo and full FDA-recommended sargramostim dose. As mentioned above, in the ongoing trial with participants who have thus far received sargramostim, there have been no serious AEs reported by participants receiving either the half dose or full dose sargramostim using the same methods proposed by this protocol. Therefore, participants will be started at the adjusted weekly dose (178.57 $\mu g/m^2/day$ SC, seven days per week, 1250 $\mu g/m^2/week$ equivalent.)

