After GM-CSF's preclinical results described above in models of AD and other neurodegenerative diseases and the association of GM-CSF with improved cognition in bone marrow transplant patients, the pilot safety and efficacy trial was initiated at the University of South Florida (USF), in which sargramostim/Leukine® was administered to mild-to-moderate AD participants for 15 days over a 19-day period (NCT01409915). At USF, the first 14 participants completed the study given placebo or sargramostim at a dosage of 125 $\mu g/m^2/day$ SC, which is half of the FDA-recommended dose. The Data Safety Monitoring Board (DSMB) met and determined that sargramostim was safe, and approved subsequent participants to receive treatment dosage of sargramostim at the full FDA-recommended dose of 250 $\mu g/m^2/day$ SC. Then with the relocation of Drs. [name] and [name] to Colorado, the trial was halted and amended to increase new enrollment to

40 participants (i.e. 20 sargramostim-treatment, 20 placebo treatment). All participants (3 at USF and 37 at CU-AMC) completed the trial either with placebo or at the full FDA-recommended dose of 250 $\mu g/m^2/day$ SC. The only AEs reported have been mild expected reactions to sargramostim, including injection site reactions, such as redness, swelling, itching, and bruising. No drug-related SAEs were reported, including no incidence of amyloid-related imaging abnormalities (ARIAs), indicating vasogenic edema (ARIA-E) and/or microhemorrhage (ARIA-H), which have been observed in all other trials testing anti-amyloid immunotherapy drugs in AD participants.

Final analysis of 40 participants showed a statistically significant treatment effect of sargramostim as assessed by MMSE, but none for the other assessments (ADAS-cog, CDR-SB, ADCS-ADL, TRAILS A).

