4.5 Specific Objectives

Improved MMSE change scores in rHuGM-CSF/sargramostim-treated participants compared to placebotreated participants. Mixed model analysis of MMSE data of the completed study of 20 sargramostim-treated participants and 20 placebo-treated participants shows a statistically significant improvement in the sargramostim-treated group at the EOT visit (a) compared to baseline (p=0.074) and to the placebo-treated group (p=0.037), and at the first follow-up visit (45 days post-EOT) compared to the placebo-treated group (p=0.0272) (b). (B) Distribution of delta MMSE scores at the EOT for random groups of 10 sargramostim-treated participants and 10 placebotreated participants. The 20 sargramostim-treated participants and 20 placebo-treated participants were divided into 10,000 random groups of 10 participants each, and the mean Mini-Mental State Exam (MMSE) scores were calculated and graphed as a delta distribution. The mean and median delta was 1.8, as was the delta of the entire 20 sargramostim-treated participants and 20 placebo-treated participants analyzed in (A) showing that the statistically significant difference between the sargramostim-treated participants and the placebo-treated participants at the EOT reflected all parts of the trial.

The specific objectives address two hypotheses: The primary hypothesis is that long-term administration of sargramostim (recombinant human GM-CSF) will be tolerated by and safe for use in participants with mild-to-moderate AD; and the secondary and exploratory hypotheses that sargramostim treatment in participants with mild-to-moderate AD will slow or halt cognitive decline and/or activities of daily living, or improve cognitive functioning and/or activities of daily living,, reduce amyloid load, inhibit progression of medial temporal atrophy (MTA), improve AD-related microstructural white matter changes, improve brain metabolic activity, improve sleep-related measures, improve indices of semantic verbal fluency, and induce changes in peripheral blood and cerebral spinal fluid (CSF) biomarkers toward levels measured in

individuals without dementia. These aims are expressed through primary, secondary and exploratory objectives with related endpoints.

Drimany Objective	Drimany Endnaint

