5.4 Double Blind Treatment Period (Baseline Visit through Visit 24)

The treatment period is double-blinded, beginning at the Baseline Visit. At the Baseline Visit, appointments for all remaining visits should be made and scheduled as close as possible to the targeted date, based on the Baseline Visit. Visits done outside the allowable window will be considered a protocol deviation. Participants who meet the entry criteria for the clinical trial will be enrolled, randomized, and receive 24 weeks of treatment with either sargramostim or placebo.

The participant will follow the schedule of 7 days (Sunday through Saturday) of subcutaneous injection (178.57 µg/m²/day sargramostim or placebo) over the course of 24 weeks, for a total maximum of 168

treatment days. The first injection will be administered at the time of baseline (randomization) visit in the site's designated facility. The participant and study partner will receive training and a schedule on how to administer additional doses at home. For the first 3 weeks, the participant will receive a weekly dose administered by their caregiver with observation by a study nurse for correct injection technique. After the first 3 weeks, the injection will be observed by a study nurse at in-person visits at the site (Wk 6, Wk 12, Wk 18). Ongoing injection technique education will be provided as needed. If the caregiver is unable to administer the in-person visit injection, the injection will instead be administered by a trained medical professional. The investigational product will be distributed weekly to the participant either at their inperson clinic visit (Baseline, week 6, week 12, week 18) or at-home visit for subsequent subcutaneous injection at home, along with a new injection diary. An empty sharps container will be provided at the baseline visit and be replaced as needed for participants/caregivers to place used syringes into at home.

At the weekly double-blind treatment period site visits (Visit 2- through Visit 24), delegated study personnel will review and record changes to conmeds, adverse events, compliance and vital signs. As well, qualified staff will review inject sites to assess for possible adverse reactions.

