9.2 Data Analysis Plan

9.2.1 Primary Objective: To assess long-term tolerability and safety of sargramostim in individuals with mild-to-moderate Alzheimer's Disease

Generally, descriptive statistics will be utilized to examine safety of participants who received sargramostim injections compared to placebo injections. Safety will be assessed by measuring the toxicity grades of AEs. These toxicity grades have been standardized by the National Cancer Institute (NCI)

Common Toxicity Criteria for Adverse Events (CTCAE Version 5.00: November 27, 2017, attached as Appendix F). Differences in toxicity grades will be compared between treatments using a Wilcoxon test for ordered outcome. MRI scans will be assessed to identify ARIAs, including vasogenic edema and microhemorrhage. Additional safety assessments will include neurological and physical examinations, vital signs and suicidality evaluations. The current study will utilize a Data Safety Monitoring Board (DSMB) to review the clinical data and ensure participant safety within the parameters of the trial.

9.2.2 Secondary Objective: To test the hypothesis that sargramostim treatment, as compared to placebo, slows or halts cognitive decline or improves cognitive function in individuals with mild-to-moderate AD.

The foremost measure used for this secondary endpoint of assessing cognitive function will be the MMSE, as it has been reported to be most sensitive to cognitive changes over time due to treatments in people ranging from late mild cognitive impairment to AD in clinical trials up to 2 years in length ¹²⁴. The cognitive assessment will be based on the participants' MMSE total score changes from Baseline to End of Treatment.

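### Section 9.1 supports power for a 24-week MMSE endpoint with a table of Day 18 differences and states no 24-week SD or effect

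*Protocol*

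**What the plan says.** Section 9.1 takes its MMSE effect from the completed pilot: "Based on results for 40 participants at the EOT, 45-day follow-up, and 90-day follow-up", an effect size "around 2–4 was predicted by the MMSE". Table 1 then lists, for differences of 2, 4, 6 and 8 points, totals of 102, 27, 12 and 9 at 2:1 with alpha 0.05 and power 0.91, 0.92, 0.92 and 0.97. Its first column is the mean treatment difference in change from "Baseline to End of Treatment (Day 18"). The sentence that introduces the table describes these same differences as changes between baseline and follow-up. The section concludes that 28 plus 14 participants will be enough for the secondary and exploratory endpoints.

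Section 4.4.2 gives the pilot's schedule: sargramostim was "administered to mild-to-moderate AD participants for 15 days over a 19-day period". Section 5.4 gives this trial's: daily injections "over the course of 24 weeks, for a total maximum of 168" treatment days. Section 9.2.2 bases the cognitive endpoint on "MMSE total score changes from Baseline to End of Treatment", and in the Schedule of Events the End of Treatment visit falls 2 to 10 days after the last dose. Section 4.5 reports the pilot difference at its own end of treatment: "The mean and median delta was 1.8".

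**The concern.** End of treatment means about three weeks in the pilot and about 24 weeks here. Table 1 uses the first meaning and the endpoint uses the second. Power depends on the difference and on the SD of change, and both may change with the interval. Section 9.1 states no SD for any time point and no expected effect at 24 weeks. Section 4.1 itself calls the pilot's treatment phase very short and says the pilot was not powered for efficacy.

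At stake is how the secondary result will be read. A reader who takes Table 1 as this trial's power calculation will think that a null MMSE result rules out more than it does, or that the power of the design at week 24 has been worked out when it has not.

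**Working it through.** **Inputs.** From Section 9.1: the differences, group sizes, alpha and power in Table 1, and the planned 28:14. From Section 4.5: pilot difference 1.8 points, p = 0.037, 20 per arm. Not in the protocol: the SD, whether the test is one- or two-sided, and any 24-week SD or effect.

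**1. Reproduce Table 1.** Two-sided normal approximation: power = Φ(δ / (SD × √(1/n₁ + 1/n₂)) − 1.96). With one SD of 2.9:

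| δ | n₁:n₂ | √(1/n₁+1/n₂) | SE | δ/SE | Power | Table 1 |
|---|---|---|---|---|---|---|
| 2 | 68:34 | 0.210 | 0.609 | 3.28 | 0.907 | 0.91 |
| 4 | 18:9 | 0.408 | 1.184 | 3.38 | 0.922 | 0.92 |
| 6 | 8:4 | 0.612 | 1.776 | 3.38 | 0.922 | 0.92 |
| 8 | 6:3 | 0.707 | 2.051 | 3.90 | 0.974 | 0.97 |

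The table is coherent. Solved row by row, the SD is 2.89, 2.91, 2.91 and 2.95. A one-sided test with SD 3.2 fits equally well (0.908, 0.922, 0.922, 0.971). A t-test does not fit with one SD: it needs 2.86, 2.80, 2.62 and 2.51. The figure of 2.9 is therefore inferred, not stated.

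**2. Compare with the pilot.** If p = 0.037 is treated as a t-test on 38 df, the SE is 0.833 and the SD is 0.833/√(2/20) = 2.63. This is only approximate, because Section 4.5 says the p-value comes from a mixed model. It is of the same order as 2.9, so the SD behind Table 1 may well be a pilot SD, but the protocol does not say so.

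**3. Compare the time points.** Day 18 fits the pilot's 19-day course. This trial's last dose is at about day 168 (24 × 7). The 2–4 point range also uses pilot follow-up at 45 and 90 days. If both are counted from end of treatment, as Section 4.5 does for the 45-day visit, the later one is near day 109 (19 + 90), off treatment. None of this is a 24-week on-treatment observation.

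**4. Power of the planned design.** For 28:14, √(1/28 + 1/14) = 0.327 and df = 40. Two-sided t-test, alpha 0.05, non-centrality δ/(SD × 0.327). The 24-week SD is an assumption; 2.9 is the value implied by Table 1 and the rest show sensitivity.

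| Assumed SD | Power at 4 points | Power at 2 points |
|---|---|---|
| 2.9 | 0.98 | 0.54 |
| 3.5 | 0.93 | 0.40 |
| 4 | 0.85 | 0.32 |
| 5 | 0.67 | 0.22 |

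At SD 4.5 the 4-point power is 0.76, so it drops below 0.80 somewhere between SD 4 and 4.5.

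**The case against.** The best defence is that nothing in Table 1 is miscalculated. It is indexed by point difference, and only an unstated SD ties it to a time. Section 9.1 does not claim 91–97% power for 42 participants; it says the table shows how many are needed for that power. The effect range also draws on follow-up visits after Day 18. The 2.9–5 SD range has no source in the protocol, and at 4 points 28:14 keeps power of about 0.85 up to SD 4. All of this stands. What it does not answer is that the only quantitative support for the power claim is headed with a time point this trial does not use, and that the adjoining text gives a different one.

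A reader might infer three stronger things that the documents do not support. The first is that 24-week power is lower than stated: this cannot be shown, because both the effect and the SD at 24 weeks are unknown. The second is that Table 1 contains an arithmetic error: it does not.

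The third is that the safety sample size is wrongly derived from the pilot. Section 9.1 says that 42 "is considered sufficient to meet the endpoint of safety and is consistent with the lack of drug related SAEs" in the pilot. That claims consistency, not derivation, and states no event rate that could be wrong. Section 4.1 discloses the pilot's short exposure, the primary safety analysis in Section 9.2.1 is mainly descriptive, and exact intervals for event rates can be left to the SAP.

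**Conclusion.** The point holds for the MMSE power statement only. Table 1 is internally sound for the Day 18 difference it names, but it is not a power calculation for change to week 24, and its heading and the accompanying text disagree on the time point. Its 91–97% figures need an explicit assumption before they can be applied here.

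The size of the gap cannot be fixed from the protocol. At 4 points the plan looks adequate unless the 24-week SD exceeds roughly 4 to 4.5. At 2 points, the lower end of the protocol's own range, power is about 0.54 even at the SD implied by Table 1, so calling it sufficient is not supported there at any SD in the assumed range. These figures assume 28 and 14 analysed participants, equal variances and a simple comparison of changes. The synopsis expects 42 completers out of about 47 randomized, whereas Section 9.1 speaks of at least 42 randomized. If only 42 are randomized and some drop out, the power of a completers' comparison falls below the figures shown. The MMSE is a secondary endpoint, so the primary safety objective is unaffected.

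**What to change.** In Section 9.1:

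- Label Table 1 as pilot Day 18 figures, and state its SD, its source and whether the test is one- or two-sided.
- Make the column heading and the sentence about follow-up name the same time point.
- Add power for 28:14 at week 24 over an SD range marked as an assumption, for example the 2- and 4-point figures worked out above.
- Replace the statement that power is sufficient with those figures.

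Optionally, add one sentence on safety precision: no events among 28 treated would leave a one-sided 95% upper limit of 1 − 0.05^(1/28) = 10.1%.

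The cost is a rewording of one section with less favourable figures at the lower effect size. No extra participants, visits or changes to treatment are needed.

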- To assess the effect of sargramostim treatment, as compared to placebo, on changes in sleep-related measures in individuals with mild-tomoderate AD.
- To assess the effect of sargramostim treatment, as compared to placebo, on changes in speech measures in individuals with mild-to-moderate AD.

Study Design:

The study is double-blind, placebo-controlled in the Alzheimer's Disease population, and will include individuals with mild AD and moderate AD, consistent with Montreal Cognitive Assessment (MoCA) score range of 4-24 at time of screening. Individuals who meet inclusion/exclusion criteria will be randomized in a double-blind manner, to receive either sargramostim (178.57 $\mu g/m^2/day$ subcutaneously 7days per week for 24 weeks) or placebo (7 days per week) in an approximate 2:1 randomization ratio.

The study population will be recruited from the Memory Disorders Clinic at the University of Colorado Hospital (UCH) as well as from the community at large.

The estimated maximum duration of participation for each individual participant is approximately 10.5 months (12 week screening phase, 24 week post-randomization double blind treatment phase, and ~6 week (45 day) post-treatment follow-up phase.

Number of Study Participants

Approximately 150 individuals and their study partners will be screened, ~47 participants randomized, with an estimated 42 individuals completing the treatment and follow-up for full analysis (~28 individuals to the sargramostim 178.57 $\mu g/m^2/day$ subcutaneously arm of the study (1250 $\mu g/m^2$ per week) and ~ 14 individuals to the placebo control arm of the study.)

Protocol Synopsis (Continued)

Key Inclusion Criteria	Individuals between age 60 and 85 years, inclusive, at time of consent who meet criteria for probable AD dementia according to the National Institute of Aging – Alzheimer's Association (NIA-AA) research framework criteria (2018), and have a diagnosis of mild or moderate AD, or a study MD provisional diagnosis consistent with mild-to-moderate AD, with a screening MoCA score between 4-24, inclusive, have (optional per PI judgment of necessity) positive plasma biomarker for Alzheimer's disease, and have positive biomarker for brain amyloid pathology by CSF assay, obtained via screening lumbar puncture, or a positive amyloid PET scan.

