7.2 Method of Treatment Assignment

Participants who meet all criteria for enrollment will be randomized into sargramostim or placebo groups at Baseline Visit, at a 2:1 ratio. This enrollment ratio was determined using the sample size power analysis, as well as to maximize recruitment and minimize attrition. The randomization schedule will be enacted and maintained at the CU Research Pharmacy (CURP), which has policies and procedures in place that describe randomization and blinding. Briefly, the pharmacy has built and implemented an Excel spreadsheet that produces random number sets that may be used for simple, weighted, block (two-, four-, or six-sized), and stratified randomization. For blinding, the pharmacy staff includes the pharmacist manager and technician. The pharmacy staff has been involved in several clinical trials that require double blinding, and double dummy. The pharmacy is an independent entity, and has the ability to ensure and maintain blinding

in any regard so that the staff at the clinical site will not know which study participants are receiving the study drug or the placebo.

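### Section 9.1 calls 42 participants sufficient for an MMSE difference of around 2–4 points, but its own Table 1 needs 102 at 2 points; 28:14 gives power of about 0.56 there

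*Protocol*

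**What the plan says.** Section 9.1 first justifies 42 participants on safety and tolerability, the primary goal. It then turns to efficacy. From the completed pilot of 40 participants (end of treatment and the 45- and 90-day follow-ups) it states that an effect size of "around 2–4 was predicted by the MMSE", and it concludes that the 42 participants "who will be recruited for this study will provide sufficient power to allow valid analyses of the secondary and exploratory endpoints".

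Table 1 in the same section lists the numbers needed at 2:1 and alpha 0.05:

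| MMSE difference | Total N | Split | Power |
|---|---|---|---|
| 2 | 102 | 68:34 | 0.91 |
| 4 | 27 | 18:9 | 0.92 |
| 6 | 12 | 8:4 | 0.92 |
| 8 | 9 | 6:3 | 0.97 |

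The table has no row for 42. Section 9.1 gives no SD, test or sidedness. The difference in Table 1 is labelled as change to Day 18, whereas section 9.2.2 bases this trial's cognitive assessment on "MMSE total score changes from Baseline to End of Treatment", which follows 24 weeks of treatment.

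Three other places bear on the point:
- Section 4.5 reports the pilot's end-of-treatment MMSE difference: "The mean and median delta was 1.8".
- Section 7.2 says of the 2:1 allocation: "This enrollment ratio was determined using the sample size power analysis", along with recruitment and attrition.
- The synopsis expects about "47 participants randomized, with an estimated 42 individuals completing the treatment and follow-up for full analysis".

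**The concern.** The sufficiency statement carries no limit, yet the table beside it contradicts it at the low end of the predicted range. At 2 points the trial has 42/102 = 41% of the number that the plan itself tabulates. MMSE change is the only secondary endpoint and its objective is framed as a hypothesis test, so readers will rely on the statement when they interpret the result.

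If power is near one half at a plausible effect, a null MMSE result says little about whether that effect exists. A reader told that power was sufficient could take the null as evidence against it.

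**Working it through.** **Inputs.** Alpha 0.05, the 2:1 ratio and the four Table 1 rows come from section 9.1, as does the planned 28:14. Two things are assumed because the protocol does not state them: a two-sample comparison of change scores, and a two-sided test (one-sided is shown as a variant).

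**Formula.** SE = SD × √(1/n₁ + 1/n₂), and power = Φ(δ/SE − 1.96).

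**Step 1: reproduce Table 1.** Solving each row for the SD gives 2.89, 2.91, 2.91 and 2.95. A single SD of 2.9 then returns:

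| δ | Split | SE | δ/SE − 1.96 | Power | Table 1 |
|---|---|---|---|---|---|
| 2 | 68:34 | 0.609 | 1.32 | 0.907 | 0.91 |
| 4 | 18:9 | 1.184 | 1.42 | 0.922 | 0.92 |
| 6 | 8:4 | 1.776 | 1.42 | 0.922 | 0.92 |
| 8 | 6:3 | 2.051 | 1.94 | 0.974 | 0.97 |

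The table is therefore internally consistent, with an implied SD of about 2.9.

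**Step 2: apply the same SD to 28:14.** SE = 2.9 × √(1/28 + 1/14) = 0.949.

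| δ | Power (normal) | Power (t-test, same SD) |
|---|---|---|
| 1.8 | 0.475 | 0.457 |
| 2 | 0.558 | 0.538 |
| 2.5 | 0.750 | 0.729 |
| 2.7 | 0.812 | 0.793 |
| 3 | 0.885 | 0.869 |
| 4 | 0.988 | 0.984 |

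**Step 3: what 28:14 can detect.**
- At 80% power: (1.960 + 0.842) × 0.949 = 2.66 points (t-test 2.73).
- At 90% power: (1.960 + 1.282) × 0.949 = 3.08 points (t-test 3.15).
- Expected 95% CI half-width: 1.96 × 0.949 = 1.86 points (1.92 with t on 40 df).
- For comparison, 80% power at 2 points needs 75 participants (50:25) by the normal approximation.

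**Step 4: does another reading rescue the sentence at 2 points?**
- One-sided 0.05: the rows imply an SD of 3.19 to 3.21. With 3.2, SE = 1.047 and 28:14 gives 0.53 at 1.8 points, 0.60 at 2, 0.89 at 3 and 0.99 at 4; the 80% detectable difference is 2.60.
- All 47 or so randomised participants analysed (about 31:16, two-sided, SD 2.9): 0.61 at 2 points.
- t-test: 0.54 at 2 points.

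Every variant leaves power at 2 points between about 0.54 and 0.61.

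**The case against.** The strongest defence is that Table 1 contains no error and the sentence is soft. It is offered as a belief, names no target power, and sits beside a table that openly shows 102 for 2 points. Power reaches 80% from 2.66 points upward, which is (4 − 2.66)/2 = 67% of the predicted range, and it is 0.885 at the midpoint. The sample size rests on safety, with the MMSE secondary.

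The 1.8-point value is also limited evidence. It comes from the end of a very short treatment course, while the 2–4 prediction also draws on follow-up results whose differences are not reported. Finally, the SD is inferred and may not apply at 24 weeks. With illustrative SDs of 2.0, 3.5 and 4.0, power at 2 points would be 0.86, 0.42 and 0.33.

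Much of this stands, and it limits the point. The safety justification is untouched, Table 1 is arithmetically sound, and the statement holds from about 2.7 points upward. The contradiction rests on the 2-point row; the 1.8 value only illustrates why the low end matters. None of it supports an unqualified claim across 2–4: the sentence is specifically about the secondary and exploratory endpoints, the only power standard in the section is 91–97%, and about 0.56 also misses 80%. Uncertainty about the 24-week SD is a further reason to state the assumptions. Two neighbouring matters are not defects in themselves: section 7.2 cites recruitment and attrition as well as power, and "Therefore, at least 42 individuals with mild-to-moderate" AD being randomised is compatible with the 47 or so in the synopsis.

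**Conclusion.** The concern holds. Over the lower part of the plan's own predicted range, 28:14 does not deliver the power that section 9.1 asserts. At 2 points power is about 0.56, so a true effect of that size would be missed about 44% of the time. At the pilot's end-of-treatment value of 1.8 points it is about 0.47. The statement is justified at 3 to 4 points (0.88 to 0.99).

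These figures rest on an SD of 2.9 back-solved from Table 1, a two-sample comparison of change scores and a two-sided 0.05 test. The conclusion does not depend on sidedness or on normal versus t. Whether the Day 18 SD and effect carry over to week 24 cannot be settled from the protocol, and the error could go either way. This should be fixed, but it calls for a qualified statement and not a different design.

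**What to change.** In section 9.1, replace the unqualified sufficiency sentence with the SD, test and sidedness used for Table 1 and the power that 28:14 provides. If the basis is two-sided 0.05 with SD 2.9, suitable text would be:

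> With 28:14 completers, power for the MMSE comparison is about 0.47 at a difference of 1.8 points, 0.56 at 2, 0.88 at 3 and 0.99 at 4. The detectable difference is about 2.7 points at 80% power and 3.1 at 90%, and the expected 95% CI half-width is about 1.9 points. These figures use the SD for change to Day 18; the SD and effect at week 24 may differ.

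If the sponsor's calculation used another SD, test or sidedness, its own figures should be substituted. At the same time, make clear in section 9.1 that 28:14 is the completer target and that about 47 are to be randomised, as in the synopsis.

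The cost is protocol wording only. Enrolment, the hypothesis-testing objective and the analysis are unchanged; the stated power becomes less favourable below about 2.7 points.
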